#### 40 Hypotheses

1 Exogenous carbohydrate oxidation will be lower at HA compared to SL during steady-state aerobic  
2 exercise at the same absolute workload, and potential regulation of diminished glucose uptake will be  
3 examined by insulin dependent or independent mechanisms.  
4

## 5 **B5. RESEARCH PLAN**

### 6 **B5.1 Research Design**

7  
8  
9 This study will be a randomized crossover control trial.

### 10 **B5.2 Research Subjects/Population(s)**

#### 11 **B5.2.1 Subject Population(s)**

12  
13  
14  
15 Subject population will be representative of active duty male service members, being in good health  
16 and recreationally active. Only males are being studied so that results from the current study can be  
17 appropriately compared to our previous study (USARIEM protocol 16-02HC). It is apparent, that sex-  
18 based differences exist during low-to-moderate intensity endurance exercise under at SL. Several  
19 investigations (16-19) have reported that females oxidize proportionately more fat and less  
20 carbohydrate than males during aerobic exercise. Sex-based differences in substrate oxidation during  
21 exercise at SL may result in differences in response to change in substrate oxidation at HA between  
22 men and women. Based on findings from the current study, follow-up work may be conducted to  
23 assess sex differences in change in substrate oxidation during exercise at HA.  
24

#### 25 **B5.2.2 Number of Subjects, Records, and/or Specimens**

26  
27 We estimate that 30 individuals will require screening in order to complete testing on the 10 volunteers  
28 necessary to reach statistical power. All screening will stop once complete data has been collected on  
29 10 volunteers. Records and specimen collection are described in the Research Procedures and Data  
30 Collection sections. During briefings and the consenting process potential volunteers will be informed  
31 that even though they may be eligible and want to participate, if we are able to obtain enough data from  
32 preceding subjects, they may not ultimately be tested.  
33

#### 34 **B5.2.3 Inclusion Criteria**

- 35
- 36 • Men aged 18 – 39 years
  - 37 • Born at altitudes less than 2,100 m (~7,000 feet; Examples include Santa Fe, New Mexico;  
38 Laramie, Wyoming; Etc.)
  - 39 • Physically active based on assessment of physical activity history (2-4 days per week aerobic  
40 and/or resistance exercise)
  - 41 • Have supervisor approval (permanent party military and civilians)
  - 42 • Willing to refrain from alcohol, smokeless nicotine products and dietary supplement use during  
43 study periods
  - 44 • Refrain from taking any nonsteroidal anti-inflammatory drugs (NSAIDs; e.g. aspirin, Advil®, Aleve®,  
45 Naprosyn®, or any aspirin-containing product) for 10 days before and at least 5 days AFTER each  
46 muscle biopsy. (\*Tylenol® or acetaminophen is ok to use if needed for discomfort)  
47

#### 48 **B5.2.4 Exclusion Criteria**

- 49
- 50 • Born at altitudes greater than 2,100 m (~7,000 feet; Examples include Santa Fe, New Mexico;  
51 Laramie, Wyoming; Etc.)

- Living in areas that are more than 1,200 m (~4,000 feet), or have traveled to areas that are more than 1,200 m for five days or more within the last 2 months (Examples include Ft. Huachuca, Arizona; Lima, Peru; Feldberg, Germany, Etc.)
- Musculoskeletal injuries that compromise exercise capability
- Metabolic or cardiovascular abnormalities (determined by resting ECG), gastrointestinal disorders (e.g., kidney disease, diabetes, cardiovascular disease, etc.)
- Medication that affects macronutrient metabolism (i.e., diabetes medications, statins, corticosteroids, etc) and/or the ability to participate in strenuous exercise
- Evidence of apnea or other sleeping disorders
- Prior diagnosis of high altitude pulmonary edema (HAPE) or high altitude cerebral edema (HACE)
- Presence of asthma or respiratory tract infections (< 1 month prior)
- Allergies or intolerance to foods (including but not limited to lactose intolerance/milk allergy), vegetarian practices, or medications (including, but not limited to, lidocaine ) to be utilized in the study
- Smoking or vaping
- History of complications with lidocaine
- Taking medications that interfere with oxygen delivery and transport (Includes sedatives, sleeping aids, tranquilizers and/or any medication that depresses ventilation, diuretics, alpha and beta blockers)
- Evidence of any physical, mental, and/or medical conditions that would make the proposed studies relatively more hazardous as determined by OMSO
- Present condition of alcoholism, anabolic steroids, or other substance abuse issues
- Anemia (HCT <38% and HBG <12.5 g/dL) and Sickle Cell Anemia/Trait
- Abnormal PT/PTT test or problems with blood clotting
- Blood donation within 8 weeks of beginning the study

### B5.3 Research Procedures

#### Study Design

This randomized crossover study will examine substrate metabolic responses to ingesting supplemental carbohydrate during steady-state aerobic-type exercise at sea level (SL) and following acute (~5 h) exposure to HA (4,300 m) conditions in 10 healthy, recreationally active adults between the ages of 18-39 yrs (**Table 1**). Following a 48-hr muscle glycogen normalization period, volunteers will complete 80-min of metabolically-matched, steady-state aerobic exercise on a treadmill, and consume 145 g of glucose ( $1.8 \text{ g}\cdot\text{min}^{-1}$ ) at SL and HA. Treadmill exercise will be performed at the same absolute workload, with speed and grade being the same at SL and HA to induce the same absolute workload between phases. SL and HA trials will occur in the USARIEM hypobaric chamber and will be separated by a minimum 7-d washout period between each protocol day. 6-6-[ $^2\text{H}_2$ ] glucose will be used as a tracer to assess glucose turnover. Indirect calorimetry, breath sampling for  $^{13}\text{C}/^{12}\text{C}$  expired in  $\text{CO}_2$ , and urine collections will be used to determine carbohydrate, fat, and protein oxidation during exercise at SL and HA. Serial blood draws will be collected during each trial to assess endocrine and circulating substrate responses to exercise, carbohydrate, and hypoxia. Muscle biopsies will be collected before and after steady-state exercise to examine intramuscular glucose transport expression and translocation, glycogen status, and activity enzyme intermediates in aerobic and anaerobic energy metabolism.

1

Study Day	SV	1	2	3	4	5	6	7	8	9	10	11	12	13	14	15
Medical Screening	X															
Body Composition		X														
Height		X														
Weight		X						X							X	
Fitness Assessment		X	X													
Blood Sampling								X							X	
Exercise Practice Sessions				X	X											
Muscle Biopsies								X							X	
Carbohydrate Depletion Exercise						X						X				
Steady-State Exercise								X							X	
Study Diet						X	X					X	X			
Carbohydrate Tracer Study								X							X	
Post Biopsy Follow-Up									X							X

2

3

4

**Table 1.** Study Timeline

5

6

Note that this is a potential timeline, specific study days and length of time to complete the study may be dependent on volunteer’s availability, so total time commitment may be longer.

7

8

9

**Research Procedures**

10

Anthropometric Data

11

Anthropometrics, performed using standardized techniques and equipment, will be used to determine volunteer eligibility and characterize study volunteers. Height will be measured to the nearest 0.1 cm using a stadiometer at screening. Body mass will be measured after an overnight fast (≥ 8 hr), using a calibrated digital scale to the nearest 0.1 kg at screening. Body mass will be measured at baseline and the morning of protocol days.

12

13

14

15

16

Body composition will be determined using dual energy x-ray absorptiometry (DEXA, DPX-IQ, GE Lunar Corporation, Madison, WI). The DEXA technique allows for the non-invasive assessment of soft tissue composition by region with a precision of 1-3% (20). The volunteer will lay face-up on the DEXA densitometer table in shorts, t-shirts, and stocking feet. Volunteers will be asked to remain motionless for the 8-10 min scan. These data will be used to calculate total body mass, fat-free mass, and fat mass. Calibration to external standards will be performed before actual data collection. The operator remains in the room with the volunteer during the scan. Measurements of body composition will be used for participant characterization and to assess if fat mass and fat-free mass are confounding variables for substrate oxidation at SL and HA.

17

18

19

20

21

22

23

24

25

26

Determination of Peak Oxygen Uptake

27

Volunteers will complete two separate maximal aerobic exercise sessions to determine peak oxygen uptake ( $\dot{V}O_{2peak}$ ) on a treadmill. Two treadmill  $\dot{V}O_{2peak}$  assessments will be conducted because HA exposure of 4,300 m produces a decrease in  $\dot{V}O_{2peak}$  of ~27% compared to SL (21). As such, volunteers will complete one treadmill  $\dot{V}O_{2peak}$  at SL and one at HA so  $\dot{V}O_{2peak}$  is known under both conditions.  $\dot{V}O_{2peak}$  will be determined using an indirect, open circuit respirator system (True Max 2400, Parvomedics, Sandy, Utah, USA). Volunteers will be instructed to fast overnight (≥ 8 hr) before testing. Volunteers will be clothed in appropriate athletic attire and perform this assessment at standard ambient indoor temperature (20-22°C) and humidity conditions (30-80%). Volunteers will be given adequate time to become familiar with the testing procedures and allowed a 3-min self-paced warm-up on the treadmill. At the start of testing, the volunteer will put on a nose clip and a mouthpiece connected to a 2-way respiratory valve, which is attached to a head piece to hold it in place. The volunteers will

28

29

30

31

32

33

34

35

36

37

38

1 begin by running for 4 min at a pace predetermined as comfortable at a 0% grade. At 4-min, the grade  
2 will be increased to 4% followed by an additional 2% every 2 min thereafter until volitional exhaustion.

3  
4 Heart rate will be monitored using a heart-rate monitor (Polar Electro Inc, Oulu, Finland) the last 30  
5 seconds of each workload during all testing. The test will be stopped immediately if the subject reports  
6 angina-like symptoms, exertional syncope, shows signs of poor perfusion (i.e., light-headedness,  
7 confusion, ataxia, pallor, cyanosis, nausea, or cold and clammy skin), or if testing equipment fails.

#### 8 9 Steady-State Treadmill Exercise Prescription

10 Results from  $\dot{V}O_{2peak}$  assessment will be used to prescribe steady-state treadmill exercise for protocol  
11 days. At SL and HA volunteers will complete 80-min of steady-state exercise on a treadmill at  $55 \pm 5\%$   
12 of their  $\dot{V}O_{2peak}$  determined at HA, performing the same absolute work under both study conditions. The  
13 speed and grade of the treadmill will be determined using the ACSM metabolic equation for walking  
14 based on desired  $\dot{V}O_2$  (22). Prior to the protocol day, participants will perform a practice session of the  
15 treadmill exercise to confirm the prescribed speed and grade are appropriate to induce target  $\dot{V}O_2$ . The  
16 speed and grade determined during the practice session will be used at SL and HA to induce the same  
17 absolute  $\dot{V}O_2$  between phases.

#### 18 19 Glycogen Normalization Period

20 A glycogen depletion protocol will be completed on a cycle ergometer, with intensity based on results  
21 from  $\dot{V}O_{2peak}$  assessment. After the warm-up period volunteers will complete 2-min of high-intensity  
22 cycling (work period) at  $90\% \dot{V}O_{2peak}$ , followed by 2-min recovery period where volunteers will cycle at  
23  $50\% \dot{V}O_{2peak}$ . This work-to-recovery ratio will be maintained until volunteers are no longer able to  
24 complete 2-min of cycling at  $90\% \dot{V}O_{2peak}$ , determined as the inability to maintain a cycling cadence of  
25 60 rpm for 15-sec. Cycling intensity will then be lowered to  $80\% \dot{V}O_{2peak}$ . When the volunteer is unable  
26 to complete 2-min of cycling at  $80\% \dot{V}O_{2peak}$ , cycling intensity will be lowered to  $70\% \dot{V}O_{2peak}$ . Once the  
27 volunteer can no longer complete 2-min of cycling at  $70\% \dot{V}O_{2peak}$ , cycling intensity will be lowered to  
28  $60\% \dot{V}O_{2peak}$ . The glycogen depletion protocol will be terminated once the volunteer is unable to  
29 complete 2-min of cycling at  $60\% \dot{V}O_{2peak}$ . For each drop in the intensity of the work period, the cycling  
30 intensity during the recovery period will be maintained at  $50\% \dot{V}O_{2peak}$  for 2-min. This exercise protocol  
31 will maximally deplete muscle glycogen stores (23). Prior to the protocol day, volunteers will perform a  
32 practice session to ensure they are familiar with the glycogen depletion protocol procedures. Following  
33 familiarization volunteers will complete a glycogen depletion protocols 48-hrs before testing.

34  
35 After completing the glycogen depletion protocol, volunteers will be fed a controlled diet providing at  
36 least  $6.0 \text{ g carbohydrate} \cdot \text{kg}^{-1} \cdot \text{d}^{-1}$  (~55-65% of total energy consumed) to ensure adequate glycogen  
37 repletion and homogeneous glycogen levels within and across volunteers between phases (SL and  
38 HA). All food and beverages (except water) will be prepared and provided by study dietitians and  
39 consist largely of military combat ration and supplemental food items. Since  $^{13}\text{C}$  will be measured from  
40 breath on protocol days, volunteers will be instructed to avoid foods high in natural abundance of  $^{13}\text{C}$ ,  
41 such as corn and cane sugar. Diets provided during the two day normalization phase will not contain  
42 these products.

[figure not shown]
#### 43 44 Altitude Chamber

45 To simulate ascension to high altitude volunteers will perform one arm of this crossover study in a  
46 hypobaric (altitude) chamber under temperate ( $20^\circ\text{C}$ , 30-50% rh;  $12\text{-}16^\circ\text{C}$  Wet Globe Bulb  
47 Temperature (WGBT)) ambient conditions. The chamber will reduce barometric pressure, and thus  
48 ambient oxygen pressure, to a value similar to that at the summit of Pike Peak, CO (4,300 m).  
49 Volunteers will be exposed to hypobaric/hypoxic conditions for 5-hrs before beginning steady-state  
50 exercise to mimic our past investigations. Total time in the chamber on the protocol day will be ~7-8-  
51 hrs. All activities within the altitude chamber will be monitored by trained study staff. The chamber is  
52 on a regular maintenance schedule and chamber performance is documented each test day.

**Exercise Protocol Day**

Two catheters will be placed into the lower arm (one in each arm). One arm will be used for infusion of 6,6-[H2] glucose tracer and the other will be used for blood sampling under resting and exercise conditions. Following an initial blood and breath sample collection to determine background enrichments, a primed, continuous infusion of 6,6-[H2] glucose will begin (prime, 82.2 μmol·kg; continuous rate, 0.78 μmol·kg·min, **Figure 4**) (24, 25). Volunteers will complete 80-min of steady-state exercise on a treadmill at 55 ± 5% of their VO2peak determined at HA, performing the same absolute work under both study conditions. V̇O2, V̇CO2, HR, and SaO2 will be measured at approximately 320, 330, 340, 360, 380, and 395 min. During exercise volunteers will consume a CHO beverage at 1.8 g·min to examine the impact of altitude exposure on exogenous carbohydrate oxidation efficiency. Drinks will contain 145 g glucose, with a total volume of 1450 mL. The drink will be consumed in four boluses throughout the 80-min of steady-state exercise (320, 340, 360, and 380-min). The first bolus will be 550 mL, with the remaining three being 300 mL. The CHO beverage consumed during exercise will be enriched with 200 mg U-C-glucose (Cambridge Isotope Laboratory, Andover, MA, USA) to increase the isotopic enrichment well above natural levels and optimize the measurement of exogenous carbohydrate oxidation. Before exercise, during the HA phase, volunteers will be exposed to hypobaric hypoxic conditions for 5-hrs to mimic our previous investigation. Muscle samples will be obtained using percutaneous muscle biopsy, taken from the vastus lateralis using a 5-mm Bergstrom needle with manual suction while the volunteer is under local anesthesia (1% lidocaine) according to the approved USARIEM SOP (26, 27). Muscle samples will be collected before (300 min) and immediately (420 min) after 80-min of steady state exercise during both the SL and HA protocol study days. The two muscle biopsy collections will occur from one incision each protocol day. Following a minimum 7-d washout period, volunteers will return to the laboratory to complete the second arm of the investigation. A total of four muscle biopsies will be conducted per volunteer, two per protocol day, with one incision made on each leg.

**Figure 4: Exercise Protocol Day**

**Figure Legend:**

- CHO = Carbohydrate
- = Carbohydrate drink
- = Muscle Biopsy
- \* = Blood Draw
- Δ = VO2, VCO2, O2 sat, heart rate
- = Steady-state (55% VO2peak at HA) exercise
- = 6,6-H2-glucose (prime, continuous infusion)
- = U-C-glucose (oral dosing)
- = breath sample
- = Urine collection

**B5.4 Data Collection**

*Blood Sampling*

Blood samples will be collected using intravenous access by a USARIEM credentialed phlebotomist on throughout protocol days under SL and HA conditions (**Figure 4**). Baseline blood sampling will occur after a 10-hr overnight fast. A total of 26 blood draws will be completed during this study taking 438 mL of blood sampled from each volunteer over the two protocol days (**Table 2**). Blood samples will be used for isotope analysis, assessment of nutrient status, hormone response, and circulating microRNA (**Table 3**).

**Table 2.** Total Volume of Blood Sampled for Protocol Days

Tube	Number of Tubes	Total Volume (mL)
7.5 mL Red Top Tube	8	60
4 mL Red Top Tube	8	32
4 mL Green Top Tube	16	64
1.2 mL Green Top Tube	16	20
6 mL Purple Top Tube	18	108
4 mL Purple Top Tube	28	112
2.6 mL Gray Top Tube	16	42
Total	110	438

**Table 3.** Blood Analytes

Analyte	Time Point (min)												
	120	180	210	240	260	280	300	320	340	360	380	400	420
Glucose 	X						X	X	X	X	X	X	X
Insulin 	X						X	X	X	X	X	X	X
Free fatty acids 	X						X	X	X	X	X	X	X
Lactate 	X						X	X	X	X	X	X	X
Glycerol 	X						X	X	X	X	X	X	X
Norepinephrine 	X						X	X	X	X	X	X	X
Epinephrine 	X						X	X	X	X	X	X	X
Hemoglobin 	X						X			X			X
Hematocrit 	X						X			X			X
 C-glucose 								X	X	X	X	X	
6,6-[  H 2 ] glucose 		X	X	X	X	X	X	X	X	X	X	X	X
c-miRNA *1	X						X			X			X
Exosomal miRNA 	X						X			X			X
PBMC +	X						X						X
Archive	X	X	X	X	X	X	X	X	X	X	X	X	X

\* Analytes: c-miRNA, circulating microRNA, +Peripheral blood mononuclear cell

Samples will be analyzed at USARIEM, Pennington Biomedical Research Center (Baton Rouge, LA) Metabolic Solutions (Nashua, NH), and The Center for Translational Research in Aging and Longevity (Little Rock, AR). All blood samples will be separated into plasma and serum through centrifugation,

1 aliquoted, and stored at  $-80^{\circ}\text{C}$  until analysis or shipment. Study samples will be collected and aliquoted  
2 at USARIEM and specific samples will be shipped on dry ice to Pennington Biomedical Research  
3 Center, Metabolic Solutions and the Center for Translational Research in Aging and Longevity. Blood  
4 sent out to other laboratories for analysis will not have any remaining samples after analysis is  
5 completed. USARIEM will retain all archive samples.  
6

#### 7 Blood Sample Processing for Enrichment

8 Blood samples for 6,6- $^{2}\text{H}_2$  glucose analysis will be collected at 180, 210, 240, 260, 280, 300, 320, 340,  
9 360, 380, 400, and 420-min to calculate plasma glucose turnover at rest and in response to exercise  
10 and carbohydrate intake under SL and HA conditions. Serial blood sampling for analysis will be  
11 collected in EDTA-coated tubes for plasma collection. The tracer/tracee ratio (6,6- $^{2}\text{H}_2$ )  
12 glucose/glucose) will be measured on the pentaacetate derivative by gas-chromatography-mass  
13 spectrometry (GCMS; Agilent Technologies, Santa Clara, CA) (24).  
14

15 Blood samples for  $^{13}\text{C}$ -glucose analysis will be collected at 320, 340, 360, 380, and 400-min to  
16 calculate the rate of plasma glucose oxidation.  $^{13}\text{C}/^{12}\text{C}$  in plasma glucose will be measured using  
17 isotope-ratio mass spectroscopy (Metabolic Solutions, Inc., Nashua, NH).  
18

#### 19 Breath Sample Processing for Isotopic Enrichment

20 The natural enrichment of the glucose ingested and the  $^{13}\text{C}/^{12}\text{C}$  in expired gas samples will be analyzed  
21 using isotope-ratio mass spectroscopy (Metabolic Solutions, Inc., Nashua, NH). Breath samples will be  
22 collected at approximately 320, 330, 340, 350, 360, 365, 370, 375, 380, 385, 390, and 395-min to  
23 determine exogenous carbohydrate oxidation using single-patient breath collection bags (Quin-Tron  
24 Instrument Company, Milwaukee, WI, USA). A baseline breath sample will also be collected prior to  
25 correct for background of naturally occurring  $^{13}\text{C}$ . All breath samples will be transferred to 10 mL  
26 evacuated tubes.  
27

#### 28 Plasma Glucose Turnover Calculations

29 For calculation of plasma glucose turnover the Steele equation with modifications for non-steady state  
30 will be used (28). Enrichment (E) will be expressed as mole percent excess (MPE); calculated as  
31  $(\text{TTR})/(1 + \text{TTR})$ , where TTR is the tracer to tracee ratio. Appropriate corrections for skewed  
32 abundance distribution and overlapping spectra will be made for the TTR of the glucose tracers, 6,6-  
33  $^{2}\text{H}_2$  glucose and U- $^{13}\text{C}$ -glucose (28). From these calculations, total glucose  $R_a$  will be comprised of  
34 rates of appearance of exogenous (i.e., ingested) glucose and of endogenous (i.e., hepatic glucose  
35 production and negligible renal glucose production or splanchnic glucose) glucose (28):  
36

$$37 \text{ Total glucose } R_a (\text{Total } R_a) = (F - ((pV \times ((C_2 + C_1) / 2) \times ((E_2 - E_1) / (t_2 - t_1)))) / ((E_2 + E_1) / 2)$$

$$38 \text{ Glucose } R_d = \text{Total } R_a - (pV (C_2 - C_1) / (t_2 - t_1))$$

$$39 \text{ Exogenous glucose } R_a (\text{Exo } R_a) = ((\text{Total } R_a + F) \times ((G_2 + GE_1) / 2) + (pV \times ((C_2 + C_1) / 2)) \times$$

$$40 ((G_2 - G_1) / (t_2 - t_1))) \text{ Endogenous glucose } R_a = \text{Total } R_a - \text{Exo } R_a$$

$$41 \text{ Metabolic Clearance Rate (MCR) = Glucose } R_d / ((C_2 + C_1) / 2)$$

42  
43 Where F represents the infusion rate of 6,6- $^{2}\text{H}_2$  glucose;  $pV$  is the effective volume of distribution for  
44 glucose,  $C_1$  and  $C_2$  are plasma glucose concentrations at  $t_1$  and  $t_2$ , respectively,  $E_1$  and  $E_2$  are plasma  
45 enrichments of 6,6- $^{2}\text{H}_2$  glucose at  $t_1$  and  $t_2$ , respectively, and  $E_d$  and  $E_p$  are tracer enrichments of U-  
46  $^{13}\text{C}$ -glucose from the test drink and plasma, respectively.  
47

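### With enrichment as mole percent excess, Total Ra already contains the infused tracer F; the exogenous Ra line adds F again and the endogenous line never removes it

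*Combined protocol and SAP*

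**What the plan says.** Plasma Glucose Turnover Calculations (B5.4) sets the convention: the Steele equation modified for non-steady state "will be used (28). Enrichment (E) will be expressed as mole percent excess (MPE); calculated as" TTR/(1+TTR), with TTR the tracer-to-tracee ratio. It describes Total Ra as made up of "rates of appearance of exogenous (i.e., ingested) glucose and of endogenous (i.e., hepatic glucose" production and minor sources). The infused tracer is not listed as a component.

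In simplified notation (bars are means over the interval t1 to t2), the printed lines are:

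- Total Ra = [F − pV·C̄·ΔE/Δt] / Ē
- Rd = Total Ra − pV·ΔC/Δt
- Exo Ra = (Total Ra + F)·Ḡ + pV·C̄·ΔG/Δt
- Endogenous Ra = Total Ra − Exo Ra
- MCR = Rd / C̄

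F is the 6,6-[²H₂] glucose infusion rate. Exercise Protocol Day (B5.3) describes "a primed, continuous infusion of" this tracer, at a continuous rate of 0.78 µmol/kg/min. The symbols in the exogenous line (G1, G2 and one printed as GE1) are not defined. E_d and E_p are defined, for drink and plasma (they "are tracer enrichments of U"-¹³C-glucose), but are not used.

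B5.8.2 plans a paired t-test of sea level (SL) against high altitude (HA) for glucose turnover.

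**The concern.** Mole percent excess divides tracer by tracer plus tracee, so a Steele equation written with it describes all glucose entering the pool, including the infusion. Adding F before multiplying by the exogenous fraction makes sense only if Total Ra excludes the infusion, which is the tracer-to-tracee convention. The section mixes the two conventions, and nothing elsewhere in the document settles which applies.

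At stake are the absolute exogenous and endogenous rates, any percentages formed from them, and changes from rest to exercise. Blood Sample Processing for Enrichment (B5.4) says turnover will be calculated at rest and in response to exercise and carbohydrate. The bias is systematic, so more volunteers would not reduce it. Two analysts could also resolve the contradiction differently and report different endogenous Ra from the same samples.

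**Working it through.** The plan states no numerical turnover result, so there is no figure to reproduce. The check is one-pool mass balance.

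**Inputs.** F = 0.78 µmol/kg/min (Exercise Protocol Day). E = TTR/(1+TTR) and the five lines above (Plasma Glucose Turnover Calculations). G is taken as E_p/E_d, which is an assumption. All true Ra values below are assumptions, in µmol/kg/min.

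**What Total Ra returns.** Let R be all glucose entering the pool: R = Endo + Exo + F.

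1. Total glucose: pV·dC/dt = R − Rd.
2. Tracer, with E a mole fraction: pV·d(E·C)/dt = F − Rd·E.
3. Expanding (2) and substituting (1): E·(R − Rd) + pV·C·dE/dt = F − Rd·E, so R = (F − pV·C·dE/dt)/E.

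This is the printed Total Ra line, so it returns Endo + Exo + F. At steady state, F/E = F/TTR + F.

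**What the other lines return.** For the oral label, pV·d(G·C)/dt = Exo − Rd·G, so Exo = R·G + pV·C·dG/dt, with no further F. Hence:

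- printed Exo Ra = Exo + F·G
- printed Endogenous Ra = (Endo + Exo + F) − (Exo + F·G) = Endo + F·(1−G)

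**Before the drink (G = 0).** Endogenous Ra is too high by 0.78.

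| Assumed true Ra | Printed | Error |
|---|---|---|
| 8 | 8.78 | 9.8% |
| 10 | 10.78 | 7.8% |
| 12 | 12.78 | 6.5% |
| 15 | 15.78 | 5.2% |

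**With the drink, steady state, G = Exo/(Endo + Exo + F).**

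| True Endo | True Exo | G | Printed Total | Printed Exo | Printed Endo |
|---|---|---|---|---|---|
| 10 | 10 | 10/20.78 = 0.481 | 20.78 | 10.38 (+3.8%) | 10.41 (+4.0%) |
| 10 | 20 | 20/30.78 = 0.650 | 30.78 | 20.51 (+2.5%) | 10.27 (+2.7%) |

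**Rest to exercise.** The endogenous error falls from F to F·(1−G), so the change is shifted downward by F·G: 0.78 × 0.481 = 0.38 and 0.78 × 0.650 = 0.51.

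**SL versus HA.** F is the same per-kg rate in both phases, so the Total Ra error cancels. The exogenous and endogenous contrasts shift, in opposite directions, by F times the SL–HA difference in G. With assumed shares of 0.6 and 0.4 that is 0.78 × 0.2 = 0.16.

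**Non-steady state.** In a simulated pool with known rates (1-min step, midpoint 40.5 min), true Total/Exo/Endo were 29.61/20.05/9.56. The printed lines gave 30.39/20.36/10.03. With F handled consistently they gave 29.61/20.05/9.56.

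At 20-min spacing the same pool (40–60 and 60–80 min) shows a separate interpolation error. Corrected Exo Ra is 21.16 and 23.15 against true midpoint values of 21.62 and 23.48; the printed line gives 21.52 and 23.61. The two errors happen to offset there, which is no reason to keep one of them. Endogenous Ra is 9.65 and 8.98 as printed, 9.23 and 8.66 corrected, and 9.13 and 8.58 true.

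**Would switching to TTR do?** Rd and MCR as printed pair all-glucose Ra with measured plasma glucose, which is consistent. Putting TTR into Total Ra removes F from both. At steady state they are then too low by F/(Ra + F): 0.78/8.78 = 8.9%, 0.78/10.78 = 7.2%, 0.78/15.78 = 4.9% and 0.78/30.78 = 2.5%. Nor is it exact in non-steady state, because the pool term would need tracee concentration and the printed line uses total C. In a simulated pool with endogenous Ra fixed at 10.00 and three successive 20-min intervals (pool conditions assumed), endogenous Ra was:

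- as printed: 10.71, 10.55, 10.42
- TTR substituted, other lines kept: 10.40, 10.38, 10.18
- mole percent excess kept, F corrected: 10.00 throughout

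**The case against.** The best case for leaving this alone is that it hardly touches what the trial tests. That is largely right. The hypothesis in B4 concerns exogenous carbohydrate oxidation, which is computed from breath ¹³CO₂ and VCO₂ (Calculations of Exogenous and Endogenous Glucose Oxidation, B5.4). The sample size in B5.8.1 also rests on oxidation. Neither uses the turnover equations. A reader might infer that the error biases the main altitude comparison; the documents do not support that, and the planned SL–HA test on Total Ra is untouched.

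A reader might also infer that the error exaggerates a suppression of endogenous production by exercise and feeding. The plan gives no Ra values and so does not establish a fall. If endogenous Ra rises, the same shift understates the rise. B5.8.2 lists time effects for concentrations and muscle outcomes, not for turnover.

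The undefined G symbols carry little weight. The equations came through PDF extraction, GE1 may be an artefact, and reading G as E_p/E_d is an inference. The F error does not depend on damaged symbols: the enrichment definition, the Total Ra line, the added F and the endogenous line are all legible.

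Finally, TTR is measured directly (Blood Sample Processing for Enrichment), so rates can be recomputed later. That makes the error recoverable, but only if someone notices it.

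**Conclusion.** The printed equations are inconsistent under the plan's own definition of enrichment. Total Ra is too high by F as a measure of exogenous plus endogenous appearance, exogenous Ra by about F·G and endogenous Ra by about F·(1−G). Rd and MCR are correct as printed.

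The size is modest: 0.78 µmol/kg/min in endogenous Ra before the drink (9.8% to 5.2% at assumed true rates of 8 to 15). In the assumed examples with the drink, the exogenous and endogenous rates are each about 2.5% to 4% too high, and the rest-to-exercise change in endogenous Ra is shifted downward by 0.38 to 0.51, whichever way it truly goes. The SL–HA contrasts in exogenous and endogenous Ra move by about 0.16 if the shares are 0.6 and 0.4.

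The direction and form of the error follow from algebra. The percentages rest on assumed Ra values and on G being E_p/E_d. The point should be corrected because turnover is a tested outcome; it does not threaten the trial's main conclusion.

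**What to change.** In Plasma Glucose Turnover Calculations:

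1. Keep mole percent excess and the Total Ra, Rd and MCR lines as printed, and state that Total Ra includes the infused tracer F.
2. Delete `+ F` from the exogenous line: Exo Ra = Total Ra·Ḡ + pV·C̄·ΔG/Δt.
3. Set Endogenous Ra = Total Ra − Exo Ra − F.
4. Define G1 and G2 (apparently E_p/E_d at t1 and t2) and check GE1 against the source document.

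Do not substitute TTR while keeping the other lines: that moves the error into Rd and MCR and leaves part of it in endogenous Ra.

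The cost is two edited lines, one sentence and one definition. No samples, measurements or tests change, and any rates already calculated can be recomputed from the stored ratios.
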